9.5.7 Biomarkers

Not applicable.

9.5.8 PK/PD

Not applicable.

9.6 Interim analyses

One interim analysis is planned for this study. At time of marketing authorization submission of the AIN457A project, the safety data of this extension study will be reported. Since the core studies have been unblinded at that stage, this interim analysis will also be unblinded. Of note, investigators, subjects and site staff will remain blinded to individual treatment group assignments.

Further interim analyses, as regarded appropriate, can be conducted (e.g., for regulatory or publication purposes).

9.7 Sample size calculation

Study CAIN457A2304 planned to randomize 918 subjects. Assuming that 5% of the subjects drop-out up to Week 12, and further 15% drop-out in CAIN457A2304 or CAIN457A2307 it is estimated that about 740 subjects will be eligible to enter this study. Assuming that the PASI 75 response rate at Week 12 in CAIN457A2304 is 80% and under the assumed drop-out rates above, about 148 subjects of each of the four treatment groups of CAIN45A2304 will be eligible to enter this extension study.

With 148 subjects per treatment group the likelihood to observe at least one occurrence of an AE with a crude incidence of 0.1% is about 14% and with a crude incidence of 1% is about 77%.

10 Ethical considerations

10.1 Regulatory and ethical compliance

This clinical study was designed and shall be implemented and reported in accordance with the ICH Harmonized Tripartite Guidelines for Good Clinical Practice, with applicable local regulations (including European Directive 2001/20/EC, US Code of Federal Regulations Title 21, and Japanese Ministry of Health, Labor, and Welfare), and with the ethical principles laid down in the Declaration of Helsinki.

10.2 Informed consent procedures

Eligible patients may only be included in the study after providing written (witnessed, where required by law or regulation), IRB/IEC-approved informed consent, or, if incapable of doing so, after such consent has been provided by a legally acceptable representative of the patient. In cases where the patient's representative gives consent, the patient should be informed about the study to the extent possible given his/her understanding. If the patient is capable of doing so, he/she should indicate assent by personally signing and dating the written informed consent document or a separate assent form. Informed consent must be obtained before conducting any study-specific procedures (i.e. all of the procedures described in the protocol). The process of obtaining informed consent should be documented in the patient source documents.

Novartis will provide to investigators in a separate document a proposed informed consent form that complies with the ICH GCP guideline and regulatory requirements and is considered appropriate for this study. Any changes to the proposed consent form suggested by the investigator must be agreed to by Novartis before submission to the IRB/IEC, and a copy of the approved version must be provided to the Novartis monitor after IRB/IEC approval.

10.3 Responsibilities of the investigator and IRB/IEC

The protocol and the proposed informed consent form must be reviewed and approved by a properly constituted Institutional Review Board/Independent Ethics Committee/Research Ethics Board (IRB/IEC) before study start. A signed and dated statement that the protocol and informed consent have been approved by the IRB/IEC must be given to Novartis before study initiation. Prior to study start, the investigator is required to sign a protocol signature page confirming his/her agreement to conduct the study in accordance with these documents and all of the instructions and procedures found in this protocol and to give access to all relevant data and records to Novartis monitors, auditors, Novartis Clinical Quality Assurance representatives, designated agents of Novartis, IRBs/IECs, and regulatory authorities as required. If an inspection of the clinical site is requested by a regulatory authority, the investigator must inform Novartis immediately that this request has been made.

10.4 Publication of study protocol and results

Novartis assures that the key design elements of this protocol will be posted in a publicly accessible database such as clinicaltrials.gov. In addition, upon study completion and finalization of the study report the results of this trial will be either submitted for publication and/or posted in a publicly accessible database of clinical trial results.

11 Protocol adherence

Investigators ascertain they will apply due diligence to avoid protocol deviations. Under no circumstances should the investigator contact Novartis or its agents, if any, monitoring the trial to request approval of a protocol deviation, as requests to approve deviations will not be granted.

This protocol defines the study objectives, the study procedures and the data to be collected on study participants. Under no circumstances should an investigator collect additional data or

conduct any additional procedures for any research related purpose involving any investigational drugs.

If the investigator feels a protocol deviation would improve the conduct of the study this must be considered a protocol amendment, and unless such an amendment is agreed upon by Novartis and approved by the IRB/IEC it cannot be implemented. All significant protocol deviations will be recorded and reported in the CSR.

Newcombe RG (1998) Two-sided confidence intervals for the single proportion: comparison of seven methods. *Statistics in Medicine*; 17: 857-872.

WHO regional office for Europe, Nutrition Unit. (1988) Classification and description of anthropometric data. EUR/ICP/NUT/125 document. Copenhagen, Denmark.

13 Appendix 1: Clinically notable laboratory values and vital signs

The following criteria will be used to define expanded limits and notable abnormalities of key laboratory tests. Notable values for blood pressure and pulse are presented in [Section 6.5.2](#). Whether action needs to be taken to address notable laboratory or vital signs values will be decided by the investigator, taking into account the overall status of the subject. No specification is foreseen as part of the study protocol.

Liver Function and Related Variables

Alanine transaminase (ALT) (SGPT):	> 3 x Upper Limit of Normal (ULN)
Aspartate transaminase (AST) (SGOT):	> 3 x ULN
Total bilirubin:	> 2 x ULN
Alkaline phosphatase:	> 2.5 x ULN

Renal Function and Electrolyte Variables

Creatinine (serum):	> 1.5 x ULN
Potassium:	> 6 mmol/L or < 3 mmol/L
Sodium:	> 160 mmol/L or < 115 mmol/L

Hematology Variables

Hemoglobin:	≥ 20 g/dL decrease from baseline
Platelet count:	< Lower Limit of Normal (LLN)
White blood cell count:	< 0.8 x LLN
Neutrophils:	< 0.9 x LLN
Eosinophils:	> 1.1 x ULN
Lymphocytes:	> 1.1 x ULN

Urinalysis Variable

Protein urine dipstick:	++*
-------------------------	-----

* ++ is ≥ 100 mg/dL

14 Appendix 2: Liver event definitions and follow-up requirements

Table 14-1 Liver Event Definitions

	Definition/ threshold
Adverse event of special interest	
Laboratory values	ALT or AST > 3 x ULN ALP > 2 x ULN TBL > 1.5 x ULN
Medically significant event (SAE)	
Laboratory values	ALT or AST > 5 x ULN (with or without TBL > 2 x ULN [mainly conjugated fraction]) ALP > 5 x ULN (with or without TBL > 2 x ULN [mainly conjugated fraction]) TBL > 3 x ULN Potential Hy's Law cases (defined as ALT/AST > 3 x ULN and TBL > 2 x ULN [mainly conjugated fraction] without notable increase in ALP to > 2 x ULN)
Adverse events	Any clinical event of jaundice (or equivalent term) ALT or AST > 3 x ULN accompanied by general malaise, fatigue, abdominal pain, nausea, or vomiting, or rash with eosinophilia Any event that links to a preferred term (PT) in the MedDRA dictionary falling under the SMQ sub-module "Drug-related hepatic disorders – severe events only" or any "Hy's law case" PT

* These events cover the following: hepatic failure, fibrosis and cirrhosis, and other liver damage-related conditions; the non-infectious hepatitis; the benign, malignant and unspecified liver neoplasms

Table 14-2 Liver Event Follow Up Requirements

Criteria	Event type	Actions required	Follow-up monitoring
Potential Hy's Law case ^a	Medically significant	Discontinue the study drug immediately Hospitalize, if clinically appropriate Report to Novartis as an SAE Establish causality	ALT, AST, TBL, Alb, PT, ALP and γGT until resolution ^c (frequency at investigator discretion)
ALT or AST			
> 8 x ULN	Medically significant	Repeat LFT within 48 hours If elevation persists, discontinue the study drug immediately Hospitalize if clinically appropriate Report to Novartis as an SAE Establish causality	ALT, AST, TBL, Alb, PT, ALP and γGT until resolution ^c (frequency at investigator discretion)
> 5 to ≤ 8 x ULN	Medically significant	Repeat LFT within 48 hours If elevation persists for more than 2 weeks , discontinue the study drug Report to Novartis as an SAE Establish causality	ALT, AST, TBL, Alb, PT, ALP and γGT until resolution ^c (frequency at investigator discretion)
> 3 x ULN accompanied by symptoms ^b	Medically significant	Discontinue the study drug immediately Hospitalize if clinically appropriate Report to Novartis as an SAE Establish causality	ALT, AST, TBL, Alb, PT, ALP and γGT until resolution ^c (frequency at investigator discretion)
> 3 to ≤ 5 x ULN (patient is asymptomatic)	AESI	Central laboratory to report to Investigator & Novartis Repeat LFT once or twice in the week If elevation persists, establish causality	Investigator discretion Monitor LFT within 1 to 4 weeks or at next visit
≤ 3 x ULN (patient is asymptomatic)	N/A	Repeat LFT at next visit	
ALP (isolated)			
> 5 x ULN	Medically significant	Repeat LFT within 48 hours If elevation persists, report to Novartis as an SAE Establish causality	Investigator discretion Monitor LFT within 1 to 4 weeks or at next visit
> 2 to ≤ 5 x ULN (patient is asymptomatic)	AESI	Central laboratory to report to Investigator & Novartis	Investigator discretion Monitor LFT within 1 to 4 weeks or at next visit

Criteria	Event type	Actions required	Follow-up monitoring
		Repeat LFT once or twice in the weekIf elevation persists, establish causality	
≤ 2 x ULN (patient is asymptomatic)	N/A	Repeat LFT at next visit	
TBL (isolated)			
> 3 x ULN	Medically significant	Repeat LFT within 48 hours If elevation persists, discontinue the study drug immediately Hospitalize if clinically appropriate Report to Novartis as an SAE Establish causality	ALT, AST, TBL, Alb, PT, ALP and γGT until resolution ^c (frequency at investigator discretion) Test for hemolysis (e.g., reticulocytes, haptoglobin, unconjugated [indirect] bilirubin)
> 1.5 to ≤ 3 x ULN (patient is asymptomatic)	AESI	Central laboratory to report to Novartis Repeat LFT once or twice in the weekIf elevation persists, establish causality	investigator discretion Monitor LFT within 1 to 4 weeks or at next visit
≤ 1.5 x ULN (patient is asymptomatic)	N/A	Repeat LFT at next visit	
Preferred terms			
Jaundice	Medically significant	Discontinue the study drug immediately Hospitalize the patient Report to Novartis as an SAE Establish causality	ALT, AST, TBL, Alb, PT, ALP and γGT until resolution ^c (frequency at investigator discretion)
“Drug-related hepatic disorders - severe events only” SMQ AE	Medically significant	Discontinue the study drug hospitalization if clinically appropriate Report to Novartis as an SAE Establish causality	Investigator discretion

^a Elevated ALT/AST > 3 x ULN and TBL > 2 x ULN but with no notable increase in ALP to > 2 x ULN

^b General malaise, fatigue, abdominal pain, nausea, or vomiting, rash with eosinophilia

^c Resolution is defined as an outcome of one of the following: return to baseline values, stable values at three subsequent monitoring visits at least 2 weeks apart, remain at elevated level after a maximum of 6 months, liver transplantation, and death.

15 Appendix 3: Blood collection log for pharmacokinetics (PK) and immunogenicity (IG)

Table 15-1 Blood collection log for PK

Visit Name	Time point	Volume (approx .)	Analyte	Sample number	Dose Reference ID/ PK collection number**
Week 52 ¹	Pre-dose	(2 mL)	AIN457 for PK	(5)	(5)
Week 64	Pre-dose	2 mL	AIN457 for PK	7	7
Week 76	Pre-dose	2 mL	AIN457 for PK	8	8
Week 104	Pre-dose	2 mL	AIN457 for PK	9	9
Week 116	Pre-dose	2 mL	AIN457 for PK	10	10
Week 128	Pre-dose	2 mL	AIN457 for PK	11	11
Week 156	Pre-dose	2 mL	AIN457 for PK	12	12
Week 208	Pre-dose	2 mL	AIN457 for PK	13	13
Week 260	672 hours*	2 mL	AIN457 for PK	14	14
Week 268 (F8)	2016 hours*	2 mL	AIN457 for PK	15	14

¹The data and sample numbering for Week 52 visit (enrollment) will have been collected as part of the end of maintenance visit (Week 52) from core study CAIN457A2304 or CAIN457A2307

* Scheduled post-dose time points for sample numbers 14 and 15 (672 hours and 2016 hours post-dose, respectively) refer to the last dose given at Week 256 as time 0.

** If a PK sample is collected at an unscheduled visit, the sample numbers will follow the pattern, 1001, 1002, etc.

Table 15-2 Blood collection log for IG

Visit Name	Time point	Volume (approx.)	Analyte	PK collection number**
Week 52 ¹	Pre-dose	(2 mL)	anti-AIN457 for IG	(504)
Week 76	Pre-dose	2 mL	anti-AIN457 for IG	506
Week 104	Pre-dose	2 mL	anti-AIN457 for IG	507
Week 128	Pre-dose	2 mL	anti-AIN457 for IG	508
Week 156	Pre-dose	2 mL	anti-AIN457 for IG	509
Week 208	Pre-dose	2 mL	anti-AIN457 for IG	510
Week 260	672 hours*	2 mL	anti-AIN457 for IG	511
Week 268(F8)	2016 hours*	2 mL	anti-AIN457 for IG	512

¹The data and sample numbering for Week 52 visit (enrollment) will have been collected as part of the end of maintenance visit (Week 52) from core study CAIN457A2304 or CAIN457A2307

* Scheduled post-dose time points for sample numbers 511 and 512 (672 hours and 2016 hours post-dose, respectively) refer to the last dose given at Week 256 as time 0.

** If an IG sample is collected at an unscheduled visit, the sample numbers will follow the pattern, 3001, 3002, etc.

16 Appendix 4: Pharmacokinetics (PK) and immunogenicity (IG) sample labeling information

16.1.1 PK sample handling

The samples must be labeled as in the following example and as provided by the central laboratory

Study code: CAIN457A2304**E1**
Site: cccc
(4 digits for the current site number)
Subject: Ccccr**rr**
(4 digits for the site number where the subject was enrolled concatenated with 3 digits for the assigned subject number. Add '0' ahead of the numbers if needed to obtain the correct number of total digits)
Sample number: As indicated in [Table 15-1](#)
Analyte: AIN457 for PK

Labels will be provided by the central laboratory with all information preprinted.

As PK samples are managed by a central laboratory, no added label should cover the original label.

16.1.2 IG sample handling

The samples must be labeled as in the following example and as provided by the central laboratory

Study code: CAIN457A2304**E1**
Site: cccc
(4 digits for the current site number)
Subject: Ccccr**rr**
(4 digits for the site number where the subject was enrolled concatenated with 3 digits for the assigned subject number. Add '0' ahead of the numbers if needed to obtain the correct number of total digits)
Sample number: As indicated in [Table 15-2](#)
Analyte: anti-AIN457 for IG

Labels will be provided by the central laboratory with all information preprinted.

As IG samples are managed by a central laboratory, no added label should cover the original label.

**Document History – Changes compared to previous version of RAP module 3.**

---

| Version          | Date      | Changes                              |
|------------------|-----------|--------------------------------------|
| 1.0              |           | First draft (initial) version        |
| Amendment
1.0 | 11-Apr-18 | To correct formatting for bookmarks. |

---

## **List of figures**

**No table of contents entries found.**

## List of abbreviations

|              |   |
|--------------|---|
| AE           | adverse event   |
| ATC          | Anatomical Therapeutic Chemical   |
| BMI          | Body Mass Index   |
| BSA          | body surface area   |
| CHMP         | Committee for medicinal products for human use  |
| CSR          | clinical study report   |
| CTCAE        | Common Terminology Criteria for Adverse Events  |
| DHP          | Data Handling Plan  |
| DLQI         | Dermatology Life Quality Index  |
| eCRF         | electronic case report/record form  |
| FAS          | Full analysis set   |
| FDA          | United States Food and Drug Administration  |
| HAQ          | Health Assessment Questionnaire ®  |
| HAQ-DI       | Health Assessment Questionnaire ® – Disability Index   |
| ICH          | International Conference on Harmonisation of Technical Requirements for Registration of Pharmaceuticals for Human Use |
| IGA          | investigator's global assessment  |
| IGA mod 2011 | Novartis Investigator's Global Assessment modified 2011   |
| IRT          | interactive response technology   |
| i.v.         | intravenous(ly)   |
| MCMC         | Markov Chain Monte Carlo  |
| MedDRA       | Medical Dictionary for Regulatory Activities  |
| NMQ          | Novartis MedDRA Query   |
| PASI         | Psoriasis Area and Severity Index   |
| PD           | protocol deviation  |
| PDS          | Programming Datasets Specifications   |
| PsA          | psoriatic arthritis   |
| PT           | Preferred Term  |
| RAP          | Report and Analysis Plan  |
| RMP          | Risk Management Plan  |

SAE                    serious adverse event  
SoR                    Start of relapse  
s.c.                   subcutaneous(ly)  
SOC                    System Organ Class

## 1 Statistical methods planned in the protocol and determination of sample size

Data will be analyzed by Novartis using SAS according to the data analysis section 9 of the study protocol which is available in [Appendix 16.1.1 of the CSR](#). Important information is given in the following sections and details are provided, as applicable, in [Appendix 16.1.9 of the CSR](#).

### 1.1 Statistical and analytical plans

The planned analysis is described in [Section 9](#) (Data Analysis) of the study protocol which is available in [Appendix 16.1.1 of the CSR](#).

This document covers the statistical and analytical plans for the final analysis. All data collected up to end of the study will be analyzed as part of final analysis.

The primary objective of the study is to assess long-term safety and tolerability of secukinumab in subjects with moderate to severe chronic plaque-type psoriasis who completed treatment in the core studies CAIN457A2304 and CAIN457A2307.

The secondary objectives are:

- To evaluate the long-term efficacy of 150 mg and 300 mg of secukinumab administered at the start of relapse versus fixed interval regimens of 150 mg and 300 mg of secukinumab respectively, in subjects with moderate to severe chronic plaque-type psoriasis who are PASI 75 responders at Week 12, with respect to PASI 75 response:
  - at Weeks 104 and 156, for subjects in the fixed interval regimens, or
  - at Weeks 92 and 144, for subjects in the retreatment at start of relapse regimen who do not require active treatment at Week 92 or 144, respectively, or
  - at Weeks 104 and 156, for subjects in the retreatment at start of relapse regimen who do require active treatment at Week 92 or 144, respectively.
- To evaluate the efficacy of secukinumab treatment regimens in subjects with moderate to severe chronic plaque-type psoriasis with respect to PASI 50/75/90/100 and IGA mod 2011 0 or 1 response over time.
- To evaluate the effects of treatment regimens with secukinumab in subjects with moderate to severe chronic plaque type psoriasis with respect to PASI score and IGA mod 2011 score over time
- To assess the effects of secukinumab treatment regimens with respect to EQ-5D score over time
- To investigate the effects of treatment regimens with secukinumab in subjects with moderate to severe chronic plaque-type psoriasis with respect to changes in DLQI over time
- To investigate the effects of treatment regimens with secukinumab in subjects with moderate to severe chronic plaque-type psoriasis with respect to DLQI 0 or 1 achievement over time
- To investigate the potential development of immunogenicity against secukinumab

- To investigate the occurrence of relapses (achieved maximal PASI improvement from baseline in core study is reduced by >50%) and rebounds in subjects on secukinumab therapy

The exploratory objectives are:

- [REDACTED]
- To explore the effects of secukinumab with respect to the HAQ-DI in subjects from core study CAIN457A2304 with psoriatic arthritis (PsA) at baseline over time

Summary statistics for continuous variables will include N, mean, standard deviation, minimum, lower quartile, median, upper quartile, maximum. Summary statistics for discrete variables will be presented in contingency tables and will include absolute and relative frequencies.

### **1.1.1 Changes to statistical methods planned in the protocol**

Table 1-11 is a modified version of table 6-3 of the protocol to clearly indicate that the area score is derived from area% without rounding.

For the maintenance of response analysis, the non-responder imputation method defined in the protocol will be dropped. The as observed result for PASI and IGA responses will be primarily looked into; the multiple imputation method will be provided as well. Assessment during follow-up period excluded.

In addition to the planned analysis on adverse events, by 1-year interval analysis on the adverse events will be provided in order to assess the occurrence of adverse events over time.

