9.4.3 Handling of missing values/censoring/discontinuations

Missing values in efficacy analyses, except for maintenance of response will not be imputed. All analyses will be based on observed values only.

For maintenance of response, please see definition below, missing values with respect to response variables based on PASI score score will be imputed with non-response regardless to the reason for missing data (e.g. premature study discontinuation, missed visit, administrative issues). Following the intent-to-treat principle for subjects who prematurely discontinue treatment, but who are observed in the follow-up period, efficacy data collected in follow-up periods will be linked to planned but missed study visits as well, following imputation schemes described in the analysis plan.

Subjects who opt to change treatment regimen or dose level and move into open-label treatment with 300 mg s.c. secukinumab every four weeks for the remainder of the trial will be considered as non-responders in the analysis of maintenance of response.

For other efficacy analyses they will not be considered after the timepoint of switching.

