## **1.8 Efficacy evaluation**

### **1.8.1 Variables**

The primary objective of the study is to assess long-term safety and tolerability of secukinumab in subjects with moderate to severe chronic plaque-type psoriasis who completed treatment in the core studies CAIN457A2304 and CAIN457A2307.

The analysis of the secondary efficacy variables will be based on the FAS.

The main secondary efficacy analysis is maintenance of response. Maintenance of response is defined as follows:

- for subjects in the fixed interval regimens, maintenance of response is defined as PASI 75 response at Weeks 104 and 156
- for subjects in the start of relapse regimens maintenance of response is defined as

- PASI 75 response at Weeks 92 and 144 for subjects who do not require active treatment at Week 92 or 144 and
- PASI 75 response at Weeks 104 and 156 for subjects who do require active treatment at Week 92 or 144.

In order to identify whether active treatment was applied at Weeks 92 and 144 the following will be utilized:

- Visit windows as in Table 1-8 (as for efficacy with date of randomization as day 1) will be applied to dosing date.
- The analysis visit Weeks 92 and 144 will be identified for dosing. The PASI assessment for the corresponding CRF visit will be selected.
- If no dosing for analysis visit Weeks 92 and 144 is identified, it is concluded that no active treatment was given. Therefore, the PASI 75 response status of the analysis visit Weeks 92 and 144 will be considered.
- For subjects with assigned dosing records at Weeks 92 and 144 but for which no corresponding PASI assessment can be assigned, non-responder imputation will be performed

Apply visit windowing to the dosing dates then find the weeks 92 and 144 dosing date. With this dosing date search for the corresponding PASI data with the same date. If there was no AIN dosing at these weeks 92 and 144 then it shall be assumed that the PASI response at Weeks 92 and 144 will be taken for the maintenance of response parameter.

[Table 1-10](#) lists the variables for the final analysis.

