### **1.8.4 Handling of missing values/censoring/discontinuations**

As observed value (Follow-up assessment excluded) will be reported primarily for both efficacy and PROs.

Response variables based on PASI score and IGA mod 2011 categories will be imputed with multiple imputation (MI) (Follow-up assessment excluded) as secondary analysis method. Summary tables for PASI scores and IGA mod 2011 categories will also be imputed using MI. Other response variables (e.g. DLQI 0 or 1 achievement) will be imputed with LOCF (Follow-up assessment excluded).

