## **1.12 Interim analyses**

Four interim analyses have been done, first one at the time of 120 days safety update; second one for 3 years IA; third one for 4 years IA; and one for 5 years IA.

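### The SAP drops the protocol's non-responder imputation and follow-up linking for maintenance of response without a stated reason, leaving no conservative estimate beside the as-observed and multiple-imputation results

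*SAP*

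**What the plan says.** Protocol 9.4.3 works from observed values in general but singles out this endpoint: "Missing values in efficacy analyses, except for maintenance of response will not be imputed". For maintenance of response, a missing PASI-based response "will be imputed with non-response regardless to the reason for missing data". For subjects who stop treatment early, citing the intent-to-treat principle, "efficacy data collected in follow-up periods will be linked to planned but missed study visits as well", by a scheme that the protocol leaves to the analysis plan.

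SAP 1.1.1 changes this: "For the maintenance of response analysis, the non-responder imputation method defined in the protocol will be dropped". As-observed results come first, multiple imputation is also given, and follow-up assessments are left out. No reason is stated. SAP 1.8.4 repeats the order: "As observed value (Follow-up assessment excluded) will be reported primarily for both efficacy and PROs", with multiple imputation as the secondary method for PASI and IGA responses. SAP 1.8.4.1 and 2.2.2 specify it: 100 imputations from a joint normal model, run separately by treatment group.

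SAP 1.8.1 treats maintenance of response as the main secondary efficacy analysis. The same section keeps one remnant of the protocol rule. For subjects with a dosing record at Weeks 92 and 144 "but for which no corresponding PASI assessment can be assigned, non-responder imputation will be performed".

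Two further facts frame the point. SAP 1.8.3 plans no hypothesis test. SAP 1.12 reports that "Four interim analyses have been done".

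**The concern.** A subject who stops treatment has no later on-treatment PASI and leaves the as-observed denominator, whatever the reason for stopping. If some stop because response is fading, the as-observed rate overstates how many of those who entered still hold their response. The protocol's rule guarded against that for this one endpoint, and the SAP removes it.

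Multiple imputation puts these subjects back into the denominator, but it fills their values from observed data in the same arm. If stopping depends on a decline that was not yet measured, both reported methods lean the same way, and nothing in the plan bounds them from below. The objective is to compare start of relapse (SoR) with fixed interval (FI), so unequal dropout would also affect the descriptive contrast.

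**Working it through.** **Plan's own figures.** The documents give no rate and no sizing for maintenance of response. Protocol 9.7 does give a planned arm size, and it reproduces: 918 × 0.95 × 0.85 = 741.3 (stated about 740), and 741.3 × 0.80 / 4 = 148.3 (stated about 148). The arm of 148 is used below only as an illustration.

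**Missing share.** The rationale for Amendment 1 (April 2014) reports about 108 discontinuations among 675 subjects: 108/675 = 16.0%. This is approximate, pooled over all arms including the open-label one, and is not the missingness at Weeks 92/104 or 144/156. A range is therefore shown.

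**Formula.** Let p be the as-observed rate and d the share missing at the endpoint visit. If every missing subject counts as a non-responder, the rate is p × (1 − d), and the gap to as-observed is p × d. All values of p are assumed.

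| p (assumed) | d | p × (1 − d) | gap, points |
|---|---|---|---|
| 70% | 16% | 58.8% | 11.2 |
| 80% | 10% | 72.0% | 8.0 |
| 80% | 16% | 67.2% | 12.8 |
| 80% | 25% | 60.0% | 20.0 |
| 90% | 16% | 75.6% | 14.4 |

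These are lower bounds on the protocol's result for the given inputs, because a linked follow-up PASI could make some discontinued subjects responders. For an intermediate case, suppose the missing respond at half the observed rate. Then p = 80% and d = 16% give 0.80 × 0.84 + 0.40 × 0.16 = 73.6%.

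**One arm of 148.** At 16% missing, about 124 are observed, and 80% of those is about 99 responders. By the score method with continuity correction (SAP 2.3.1):
- As observed: 99/124 = 79.8% (95% CI 71.5 to 86.3).
- Every missing subject a non-responder: 99/148 = 66.9% (58.6 to 74.3).

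**Regimen contrast (all inputs assumed).**
- Both regimens at 80%, with 12% (FI) and 20% (SoR) missing: the observed gap is 0; counting the missing as non-responders, it is 0.704 − 0.640 = 6.4 points.
- FI 80% and SoR 70%, both with 16% missing: the gap goes from 10 to 0.672 − 0.588 = 8.4 points.
- FI 80% with 10% missing and SoR 70% with 25% missing: the gap goes from 10 to 0.720 − 0.525 = 19.5 points.

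The contrast can widen or shrink. The documents give no per-arm figures to say which.

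**SAP 1.1.1 against 1.8.1.** The first drops non-responder imputation for this analysis without exception. The second applies it where dosing is recorded at Week 92 or 144 but no PASI matches, in a step whose purpose is to classify SoR subjects. Both cannot stand as written. The affected cell should be almost empty: Protocol 6 (order of assessments) and 6.4.2 require the PASI to be entered before the IRT assigns drug.

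**The case against.** The change is declared in the section meant for it. It brings this endpoint into line with the observed-values approach that the protocol used for its other efficacy analyses. The primary objective is safety, Protocol 9.4 names no key secondary variable, and nothing is tested, so there is no type I error to protect. Non-responder imputation has its own downward bias, since it counts missed visits and administrative gaps as failures. All of this stands. It is why making non-responder imputation the lead method again is a trade-off and not a correction.

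Several stronger readings do not hold:

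- **The endpoint is estimated only in patients who stayed.** Multiple imputation is also provided. It uses each subject's own earlier values, and SAP 1.8.4.1 includes subjects with no post-baseline data. The as-observed rate also keeps anyone assessed at the visit who leaves later. What remains is that the method assumes missing at random within arm. The SAP does not show how it applies to the conditional Week 92/104 and 144/156 definition, and the extra sensitivity analyses that SAP 2.2.2 mentions for higher dropout have no threshold or method.
- **Interim results drove the change.** The protocol expressly calls only the submission safety interim unblinded (3.5 and 9.6). SAP 1.12 gives neither the blinding status nor the efficacy content of the four interims. SAP version 1.0 is undated, and the amendment of 11-Apr-18 corrects formatting only. Subjects were unblinded at Week 156, so later looks may well have been unblinded, but nothing links them to this decision.
- **Unequal rules bias the FI–SoR comparison.** The remnant in SAP 1.8.1 touches few subjects if any, and would lower the SoR rate. It is a wording conflict, with no demonstrated bias.
- **The reported rate is inflated.** This is plausible but not shown. The documents give no reasons for the discontinuations.

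**Conclusion.** The point holds as one about reporting and consistency. For its main secondary efficacy analysis the SAP withdraws a missing-data rule that the protocol had reserved for that endpoint, reverses the use of follow-up data, and gives no reason. The lead estimate rests on subjects with on-treatment PASI at the endpoint visit, the second method assumes missing at random, and no conservative analysis is committed to.

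For assumed as-observed rates of 70% to 90% and 16% missing, the most the missing subjects could take off the rate is about 11 to 14 points. At an assumed 80%, it is 8 points with 10% missing and 20 points with 25%. These sizes rest on assumed response rates and on a pooled, approximate dropout figure from April 2014, and they set aside follow-up linking. The harm is a possibly optimistic descriptive rate and an uncertain regimen contrast. The conflict between SAP 1.1.1 and 1.8.1 is real but probably affects very few subjects.

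**What to change.** 1. Report the protocol's non-responder analysis of maintenance of response for all four randomised arms, under one rule for FI and SoR, beside the as-observed and multiple-imputation results. It need not lead.
2. Include the protocol's follow-up linking, and write down the mapping of follow-up PASI to missed visits, which the protocol left to the analysis plan.
3. Give the number missing by arm at Weeks 92, 104, 144 and 156.
4. Reconcile SAP 1.1.1 with the remaining non-responder step in 1.8.1.
5. State the reason for the change and the date it was decided.

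The cost is roughly one extra table from data already held, plus a few sentences of specification. The downside is a conservative, less favourable rate, which should be labelled as such.
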